3.11 Patient-reported outcomes

Not applicable.

3.14 Interim analysis

No formal interim analysis is planned for this study. However, summaries of safety and PK data will be produced to support the regular safety monitoring conducted by the DMC and the confirmation of RP2D. Efficacy data may also be analyzed when all patients (Phase I and Phase II) have completed 24 weeks (approximately 6 months) of treatment or discontinued earlier. The final analysis will be conducted when all patients have completed Month 24 (i.e., the end of the long-term follow-up period), unless the patients discontinue earlier.

In this clinical trial it is not planned to test specific efficacy hypotheses but to provide estimates of efficacy endpoints for the pediatric study population and therefore no-alpha adjustment will be made for earlier estimates of efficacy endpoints. However, the data for the primary efficacy assessment, ORR at Day 28 will already be final once all patients have completed 6 months of treatment.

4 Sample size calculation

In Phase I, 5 patients will be enrolled to each age groups 2 and 3. A minimum of 5 patients in Group 1 will also undergo extensive PK sampling during Phase II. Should one or more of the 5 patients not be evaluable for PK analysis, additional patients may be enrolled to ensure a minimum of 5 evaluable PK profiles for Groups 1, 2 and 3.

A comparison of PK parameters (Cmax) from 5 pediatric patients (in Groups 2 and 3 separately) to ~25 adult patients (from study CINC424C2301) will be performed. With expected similarity in the point estimates across groups (geo-mean ratio, GMR = 1), and accounting for expected higher variability in the pediatric patients (CV% ~55.7%, ([Loh et al 2015](#), detailed data on file) compared to ~40% in adults), the confidence interval for a GMR of 1 would be [0.609;1.641] which demonstrates clinically relevant comparability of exposure to adult exposure (within 2-fold).

Therefore, with a minimum of 5 evaluable profiles in each of Groups 2 and 3, combined with 5 evaluable profiles from Group 1 and further sparse PK samples in the Phase II of the study, there is sufficient precision to support the PK objectives of the study.

Should the exposure in Group 2, 3 or 4 not be confirmed following the PK sampling in at least 5 patients, additional patients will be enrolled in that specific age group until the dose/exposure is confirmed (i.e., selection of the RP2D for those ages based on exposure and safety review by the DMC). Once the RP2D is selected for Groups 2 and 3 any further eligible patients between the ages of 2 years and 12 years will be enrolled into the Phase II, and Group 4 will begin enrolling patients in the Phase I.

Although several studies of treatments for aGvHD and SR-aGvHD have included pediatric patients, it is difficult to find recent estimates for steroid response in de novo aGvHD pediatric

patients or BAT response in SR-aGvHD pediatric patients. A review of 443 patients (including 175 patients < 20 years, reported a CR/PR rate of 55% at Day 28, no association with ORR rate and patient age was found ([MacMillan et al 2010](#)). Other papers report response rates in the ranges 50-60% for de novo and SR-aGvHD ([Martin et al 2012](#)).

The sample size for the Phase II objective of measuring ORR at D28 is 45 patients regardless of age. Of these, there must be at least 20% of the patients with treatment naïve aGvHD and 40% of the patients with SR-aGvHD to ensure the sample is representative of the study population. The remaining can be filled with either diagnosis. Any patient receiving the confirmed RP2D during the Phase I will be counted towards the 45 patients.

The sample size calculation for the Ph II activity objective is based on the ORR at Day 28. Assuming the true ORR at Day 28 of the study population is 80%, an overall sample size of 45 patients would have 90% probability to have a 90% CI for ORR with lower limit $\geq 60\%$. In addition, considering the Saw-Toothed behavior of power waving for single binomial proportion using an exact method ([Chernick and Liu 2002](#)). A minimum sample size of 45 subjects would provide >85% of the probability to have a 90% CI with lower limit $\geq 60\%$. [Table 12-2](#) provides estimates of power, minimum number of responders required to have a 90% CI with lower limit of $\geq 60\%$ and two-sided 90% Clopper-Pearson CIs for various sample size. Patients treated at the RP2D from the Phase I contribute to this analysis.

Table 4-1 Probability to have a 90% CI with lower limit $\geq 60\%$ and 90% confidence intervals for different number of patients

Sample size	Minimum No. of responders	Response Rate	Probability to have a 90% CI with lower limit $\geq 60\%$	90% CI	
37	28	0.76	0.809	0.614	0.867
38	29	0.76	0.784	0.623	0.871
39	29	0.74	0.859	0.604	0.854
40	30	0.75	0.839	0.613	0.858
41	31	0.76	0.818	0.621	0.861
42	31	0.74	0.882	0.604	0.846
43	32	0.74	0.864	0.612	0.849
44	33	0.75	0.846	0.620	0.853
45	33	0.73	0.901	0.604	0.838
46	34	0.74	0.886	0.612	0.842
47	35	0.74	0.869	0.619	0.846
48	35	0.73	0.916	0.604	0.832
49	36	0.73	0.903	0.612	0.835
50	37	0.74	0.889	0.619	0.838

5 Change to protocol specified analyses

No change from protocol

6 Appendix

6.1 Imputation rules

6.1.1 Study drug

The following rule should be used for the imputation of the dose end date for a given study treatment component:

Scenario 1: If the dose end date is completely missing and there is no EOT page and no death date, the patient is considered as on-going:

The patient should be treated as on-going and the cut-off date should be used as the dose end date.

Scenario 1 should not be applied for final CSR. All patients should have EOT page complete before the Database lock for Final CSR

Scenario 2: If the dose end date is completely or partially missing and the EOT page is available:

Please note that date of assessment on EOT eCRF might be very different from last date of dose.

Case 1: The dose end date is completely missing, and the EOT completion date is complete, then this latter date should be used.

Case 2: Only Year(yyyy) of the dose end date is available and yyyy < the year of EOT date:

Use Dec31yyyy

Case 3: Only Year(yyyy) of the dose end date is available and yyyy = the year of EOT date:

Use EOT date

Case 4: Both Year(yyyy) and Month (mm) are available for dose end date, and yyyy = the year of EOT date and mm < the month of EOT date:

Use last day of the Month (mm)

All other cases should be considered as a data issue and the statistician should contact the data manager of the study.

After imputation, compare the imputed date with start date of treatment, if the imputed date is < start date of treatment:

Use the treatment start date

Patients with missing start dates are to be considered missing for all study treatment component related calculations and no imputation will be made. If start date is missing then end-date should not be imputed.

6.1.2 AE, ConMeds and safety assessment date imputation

Table 5-1 Imputation of start dates (AE, CM) and assessments (LB, EG, VS)

Missing Element	Rule
day, month, and year	
 No imputation will be done for completely missing dates
day, month	
 If available year = year of study treatment start date then 
 If stop date contains a full date and stop date is earlier than study treatment start date then set start date = 01JanYYYY Else set start date = study treatment start date. If available year > year of study treatment start date then 01JanYYYY If available year < year of study treatment start date then 01JulYYYY
day	
 If available month and year = month and year of study treatment start date then 
 If stop date contains a full date and stop date is earlier than study treatment start date then set start date= 01MONYYYY. Else set start date = study treatment start date. If available month and year > month and year of study treatment start date then 01MONYYYY If available month and year < month year of study treatment start date then 15MONYYYY

Table 5-2 Imputation of end dates (AE, CM)

Missing Element	Rule (* if end date of the on-treatment period not > (death date, cut-off date, withdrawal of consent date))
day, month, and year	
 Completely missing end dates (incl. ongoing events) will be imputed by the end date of the on-treatment period*
day, month	
 If partial end date contains year only, set end date = earliest of 31DecYYYY or end date of the on-treatment period *
day	
 If partial end date contains month and year, set end date = earliest of last day of the month or end date of the on-treatment period*

Any AEs and ConMeds with partial/missing dates will be displayed as such in the data listings.

Any AEs and ConMeds which are continuing as per data cut-off will be shown as 'ongoing' rather than the end date provided.

The above imputations are only used for analyses of time to and duration of AEs and concomitant medications.

6.1.2.1 Other imputations

Incomplete date of initial diagnosis of aGvHD

Missing day is defaulted to the 15th of the month and missing month and day is defaulted to 01-Jan.

6.2 AEs coding/grading

Adverse events are coded using the Medical dictionary for regulatory activities (MedDRA) terminology.

The latest available MedDRA version at the time of the analyses should be used. The MedDRA version used should be specified in the footnote of relevant tables.

AEs will be assessed according to the Common Terminology Criteria for Adverse Events (CTCAE) version 4.03.

The CTCAE represents a comprehensive grading system for reporting the acute and late effects of cancer treatments. CTCAE grading is by definition a 5-point scale generally corresponding to mild, moderate, severe, life threatening, and death. This grading system inherently places a value on the importance of an event, although there is not necessarily proportionality among grades (a grade 2 is not necessarily twice as bad as a grade 1).

6.3 Laboratory parameters derivations

Grade categorization of lab values will be assigned programmatically as per NCI Common Terminology Criteria for Adverse Events (CTCAE) version 4.03. The calculation of CTCAE grades will be based on the observed laboratory values only, clinical assessments will not be taken into account. The criteria to assign CTCAE grades are given in Novartis internal criteria for CTCAE grading of laboratory parameters. The latest available version of the document based on the underlying CTCAE version 4.03 at the time of analysis will be used. For laboratory tests where grades are not defined by CTCAE v4.03, results will be graded by the low/normal/high (or other project-specific ranges, if more suitable) classifications based on laboratory normal ranges.

A severity grade of 0 will be assigned for all non-missing lab values not graded as 1 or higher. CTCAE Grade 5 is not defined for laboratory values. For laboratory tests that are graded for both low and high values, summaries will be done separately and labelled by direction, e.g., sodium will be summarized as hyponatremia and hypernatremia.

Imputation Rules

CTC grading for blood differentials is based on absolute values. However, this data may not be reported as absolute counts but rather as percentage of WBC.

The following rules will be applied to derive the WBC differential counts when only percentages are available for a xxx differential

$$\text{xxx count} = (\text{WBC count}) * (\text{xxx \%value} / 100)$$

Further derivation of laboratory parameters might be required for CTCAE grading.

CTC grades for the derived absolute WBC differential counts (neutrophils, lymphocytes) and will be assigned as described above for grading.

6.4 Statistical models

6.4.1 Primary analysis

Confidence interval for ORR

Responses will be summarized in terms of percentage rates with two-sided 90% confidence interval using exact binomial confidence interval (implemented using SAS procedure FREQ with EXACT statement [\[Clopper and Pearson 1934\]](#)).

6.4.2 Key secondary analysis

Same instruction for the confidence interval for ORR as in section 5.4.1

6.4.3 Definition of new or additional systemic treatment for aGvHD

The data source to search for the new or additional systemic therapy is the CRF of “Prior and Concomitant Medication” (CONMED) or CRF “Prior or Concomitant non-drug therapies/procedures” and “Study treatment CNI”.

Systemic therapies are identified using the Route (if CMROUTE is Intramuscular, Intravenous, Oral, Subcutaneous, or Parenteral).

Any of the following therapies represent new or additional systemic therapy for aGvHD:

- Any CNI therapy being initiated newly as ‘treatment for aGvHD’ after the baseline (as recorded on Study treatment CNI and with indication = “treatment for aGvHD” on CONMED page). That means when a subject starts a new systemic therapy during study treatment for the indication ‘treatment for aGvHD’, or a subject received the same therapy before as prophylaxis and then changed to treatment of aGvHD as indication, this will be considered as new or additional systemic treatment.

CNI therapy given as ‘treatment for aGvHD’ that started after Day 1 will be considered as new or additional systemic treatment, even if the same therapy was given as treatment for aGvHD already before start of study treatment but the patient was not receiving such therapy on Day 1. Whereas a stop of such therapy after Day 1 and later re-start of the same therapy will not be considered as new or additional therapy.

Change of the drug within the defined group of CNIs or only change of the dose is not considered as new CNI treatment.

- Any other systemic treatments (excluding CNI and steroids) being initiated newly as ‘treatment for aGvHD’ or after the baseline and documented in CONMED (according to the same definitions as for CNI treatments above).
- Any other non-drug therapy/procedure being initiated newly as ‘treatment for aGvHD’ after the baseline (according to the same definitions as for CNI above) and documented on concomitant non-drug therapies/procedures (e.g. ECP).

Changes in the systemic corticosteroid therapy (captured on study treatment eCRF), e.g. change of the drug, the dose or any interruption and re-start, will not be taken into account for identification of new or additional systemic therapy, nor will any other corticosteroid therapy (in CONMED) be considered.

7 Reference

1. Anderson JR, Cain KC and Gelber RD (1983). Analysis of survival by tumor response. *Journal of Clinical Oncology*, 1(11), 710-719.

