Patients who discontinue from study or withdraw their consent/oppose the use of their data/biological samples should be scheduled for a final evaluation visit if they agree, as soon as possible, at which time all of the assessments listed for the final visit will be performed. At this final visit, all dispensed investigational product should be reconciled, and the adverse event and concomitant medications not previously reported must be recorded on the CRF. As per [Section 4.6](#), during a Public Health emergency as declared by Local or Regional authorities i.e. pandemic, epidemic or natural disaster that limits or prevents on-site study visits, alternative methods of providing continuing care may be implemented by the investigator as the situation dictates.

Table 8-1 Assessment Schedule

Period	Screening	Treatment ¹					Safety Follow-up	Long Term Follow-up ²		
Visit Name	Screening	Day 1	Week 1-Week 8 (Weekly)	Week 12-Week 24 (Monthly)	Week 28-Week 48 (only in the case of taper or aGvHD flare, monthly)	EOT (Week 24/Week 48) ³	Safety Follow-up visit	Month 12	Month 18	Month 24
Weeks	-4	1	1 to 8	12 to 24	28 to 48	48	0	53	78	105
Days	-28 to -1	1	7 to 56	84 to 168	196 to 336	-	Last dose [contact]
Study Informed Consent/Assent	X									
Inclusion / Exclusion criteria	X									
Disease history (alloSCT and aGvHD history, CIBMTR risk assessment)	X									
HCT-Specific Co-Morbidity Index Score	X									
Demography	X									
Other relevant Medical History	X									
Prior/Concomitant Medications	X (From screening until safety follow up)									
IWRS/IRT (Registration, EOT)	X	X	X (Monthly)	X	X	X				
Physical Examination	S	S	S	S	S	S				
Body Height	X	X		X (Week 24)		X		X	X	X
Body Weight	X	X	X	X	X	X		X	X	X
Vital Signs	X	X	X	X	X	X				
Hematology	X	X	X	X	X	X				
Chemistry	X	X	X	X	X	X				

Period	Screening	Treatment ¹					Safety Follow-up	Long Term Follow-up ²		
Visit Name	Screening	Day 1	Week 1- Week 8 (Weekly)	Week 12- Week 24 (Monthly)	Week 28- Week 48 (only in the case of taper or aGvHD flare, monthly)	EOT (Week 24/Week 48) ³	Safety Follow-up visit	Month 12	Month 18	Month 24
Weeks	-4	1	1 to 8	12 to 24	28 to 48	48	0	53	78	105
Days	-28 to -1	1	7 to 56	84 to 168	196 to 336	-	Last dose [contact]
Coagulation	X	X	X	X	X	X				
Hepatitis viral serology testing (HBV, HCV)	X									
Hepatitis viral load (HBV, HCV)	X	X (Every 6 months while on ruxolitinib treatment)								
Urinalysis	X	X	X	X	X	X				
Pregnancy test (serum)	S ⁵					S ⁵	S ⁵			

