9.1.5 Follow up for safety evaluations

1. Safety Follow-up Visit

All patients must have a follow-up visit for safety evaluations 30 days (+ 3 day visit window) following the last dose of study treatment based on discontinuation from Treatment Period.

At the Safety Follow-Up visit, adverse events and therapies after treatment discontinuation will be reviewed. In addition, serum pregnancy will be collected for female patients of child-bearing potential. Refer to [Table 8-1](#). Patients who remain on ruxolitinib at Week 48 and obtain access to ruxolitinib outside of the study will not complete the safety follow-up visit since study treatment will continue.

1. Long-term safety Follow-up

All patients who discontinue study treatment (responders, non-responders, completing or prematurely discontinued from treatment period for any reasons as outlined above) will enter in the Long Term Follow-Up period, which lasts up to 24 months from start of study treatment (Day 1). Patients who prematurely discontinue ruxolitinib prior to Week 24 (without achieving CR or PR), must have assessments performed at the end of Week 24 ([Table 8-1](#)) and subsequently enter the Long Term follow-up period.

Visits are scheduled every six months (+/- 1 month from scheduled visit) starting Month 12 followed by subsequent visits at Month 18 and Month 24. Patients who may have an End of Treatment at Week 48 due to extended taper or aGvHD flare, will have the long-term follow up at Month 18 and 24 only.

Information to be collected during Long-Term follow-up is detailed in [Table 8-1](#). Data collected should be entered in the appropriate eCRF. Unscheduled visits may be performed as necessary. Additional assessments may be done as per institutional guidelines at investigator's discretion at any time during the trial.

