Week 32	Study Day 224	Study Days 211 – 238
Week 36	Study Day 252	Study Days 239 – 266
Week 40	Study Day 280	Study Days 267 – 294
Week 44	Study Day 308	Study Days 295 – 322
Week 48	Study Day 336	Study Days 323 – 350
Month 12*	Study Day 365	Study Days 351 – 455
Month 18*	Study Day 546	Study Days 456 - 636
Month 24*	Study Day 730	Study Days 637 - 820

Study Day 1 = start date of study treatment;

EOT assessments are mapped to the time points as appropriate;

Last contact date

The last contact date will be derived for patients not known to have died at the analysis cutoff using the last complete date among the following:

Table 3-2 Last contact date data sources

Source data	Conditions
Last contact date/last date patient was known to be alive from Survival Follow-up page	Patient status is reported to be alive, lost to follow-up or unknown.
Start/End dates from new aGVHD treatment since discontinuation from study treatment	Non-missing medication/procedure term.
Start/End dates from drug administration/concomitant medication record	Non-missing dose. Doses of 0 are allowed.
Disposition event date from the disposition log page	No condition.

Source data	Conditions
- aGvHD assessment date - any specific efficacy assessment date if available (e.g., cGvHD assessment, graft failure assessment, second primary malignancy assessment, hematologic disease relapse/progression assessment)	Non-missing assessment
Laboratory/PK collection dates/ [REDACTED] [REDACTED]	Sample collection marked as 'done'.
Vital signs date	At least one non-missing parameter value
Collection date of acceptability and palatability questionnaire	Assessment performed is "Yes" [REDACTED]
Start/End dates of AE	Non-missing verbatim term

The last contact date is defined as the latest complete date from the above list on or before the data cutoff date. The cutoff date will not be used for last contact date, unless the patient was seen or contacted on that date. No date post cutoff date will be used. Completely imputed dates (e.g. the analysis cut-off date programmatically imputed to replace the missing end date of a dose administration record) will not be used to derive the last contact date. Partial date imputation is allowed for event (death)/censoring coming from 'Survival information' eCRF.

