Event-free survival is defined as the time from the study treatment start date to the date of hematologic disease relapse/progression, graft failure or death due to any cause. If a patient is not known to have any event, then EFS will be censored at the latest date the patient was known to be alive (last contact date on or before the cut-off date).

- **Failure Free Survival (FFS)**

Failure-free survival is defined as the time from the study treatment start date to date of hematologic disease relapse/progression, non-relapse mortality (NRM) or addition of new systemic aGvHD treatment. Each type of failure as a competing risk for the other two, and onset of chronic GvHD is considered as a competing risk for all three types of failure. If a patient is not known to have any event or competing risk, then FFS will be censored at the latest date the patient was known to be alive (last contact date on or before the cut-off date).

- **Non-relapse mortality (NRM)**

Non-relapse mortality is defined as the time from the study treatment start date to date of death not preceded by hematologic disease relapse/progression. Hematologic disease relapse/progression is considered a competing risk for NRM with the date of hematologic disease relapse/progression being the earlier of documented hematologic disease relapse/progression or institution of therapy to treat potential hematologic disease relapse/progression. If a patient is not known to have died or to have relapsed/progressed, then NRM will be censored at the latest date the patient was known to be alive (last contact date on or before the cut-off date).

- **Incidence of Malignancy Relapse/Progression (MR)**

Malignancy relapse/progression is defined as the time from the study treatment start date to date of hematologic malignancy relapse/progression. Deaths not preceded by hematologic

malignancy relapse/progression are competing risks. If a patient is not known to have event or competing risks, then MR will be censored at the latest date the patient was known to be alive (last contact date on or before the cut-off date).

- **Cumulative steroid dosing until Day 56**

The weekly cumulative steroid dose will be calculated for each patient up to Day 56 and the overall cumulative steroid dose will be calculated for each patient at Day 56. In addition, the proportion of patients with any dose reduction and any dose reduction of at least 50% in corticosteroids from baseline until EOT will be provided.

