3.7.2 Statistical hypothesis, model, and method of analysis

All secondary efficacy endpoint analyses will be analyzed using the EES.

- **Overall Response Rate at Day 14**

Overall response rate at Day 14 will be calculated based on the local investigators review of aGvHD assessment data. They will be summarized using descriptive statistics (N, %) with two-sided exact binomial 90% CIs [Clopper and Pearson 1934].

- **Best Overall Response (BOR)**

BOR up to and including Day 28 will be calculated based on the local investigators review of aGvHD assessment data. They will be summarized using descriptive statistics (N, %) with two-sided exact binomial 90% CIs [Clopper and Pearson 1934]. BOR up to cut-off date will also be analysed in the same way.

- **Duration of response (DOR)**

The estimated cumulative incidence rates and 95% confidence intervals at 1, 2, 6, 12, 18 and 24 months will be presented. The cumulative incidence curve will be plotted. DOR will be summarized for all patients in the EES with overall response of CR or PR at Day 28.

- **Overall survival (OS)**

The OS distribution will be estimated using the Kaplan-Meier method, and the Kaplan-Meier curves, medians, 1, 2, 6, 12, 18 and 24 month survival estimates and 95% confidence intervals [Brookmeyer and Crowley 1982] will be presented.

- **Event Free Survival (EFS)**

The EFS distribution will be estimated using the Kaplan-Meier method, and the Kaplan-Meier curves, medians, 1, 2, 6, 12, 18 and 24 month survival estimates and 95% confidence intervals [Brookmeyer and Crowley 1982] will be presented.

- **Failure Free Survival (FFS)**

Cumulative incidence curve for FFS as well as estimates at 1, 2, 6, 12, 18 and 24 months with 95% confidence intervals will be presented, accounting for onset of chronic GvHD as the competing risk.

In addition, the cumulative incidence of each of the three components considering the other two components as a competing risks will be estimated. Onset of chronic GvHD is considered as a competing risk for all three types of failure.

- **Non-relapse mortality (NRM)**

The cumulative incidence curve for NRM as well as estimates at 1, 2, 6, 12, 18 and 24 months with 95% confidence intervals will be presented.

- **Incidence of Malignancy Relapse/Progression (MR)**

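### The SAP's search for new systemic aGvHD therapy omits the post-discontinuation treatment source, so 12- to 24-month failure-free survival could miss failures

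*SAP*

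**What the plan says.** - **Event.** SAP 3.7.1 makes FFS a three-part endpoint: relapse or progression, "non-relapse mortality (NRM) or addition of new systemic aGvHD treatment".
- **Horizon.** SAP 3.7.2 asks for a "Cumulative incidence curve for FFS as well as estimates at 1, 2, 6, 12, 18 and 24 months with 95% confidence intervals".
- **Censoring.** Under SAP 3.7.1, if no event or competing risk is known, "then FFS will be censored at the latest date the patient was known to be alive", meaning the last contact date on or before cut-off.
- **How the therapy event is found.** SAP 6.4.3 states: "The data source to search for the new or additional systemic therapy is the CRF of", and goes on to name prior and concomitant medication, non-drug therapies and procedures, and study-treatment CNI. SAP 3.4.2.6 uses the same derivation for the additional-therapy table.
- **The other source.** SAP 3.1.1, Table 3-2, lists "Start/End dates from new aGVHD treatment since discontinuation from study treatment" as an input to last contact date. It has its own row, separate from the drug administration and concomitant medication row.
- **Collection schedule.** In Protocol Table 8-1 the prior and concomitant medication row reads "X (From screening until safety follow up". Protocol 9.1.5 places that visit "30 days (+ 3 day visit window) following the last dose of study treatment". The Month 12, 18 and 24 columns have no therapy row, and the long-term data listed in Protocol 3.3 do not include new aGvHD therapy.

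**The concern.** The protocol ties the new-therapy event to stopping ruxolitinib. A patient who needs new systemic aGvHD treatment must discontinue (Protocol 6.1.5.1.1, 9.1.1), and a patient without response at Day 28 must stop and be treated otherwise (Protocol 6.1.5). A record of aGvHD treatment since discontinuation is therefore where one would expect to find many of these events, and it is the one source the event rule does not name.

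Two consequences follow if a therapy start sits only in that source. It is not counted as a failure. And because Table 3-2 uses its dates for last contact, and FFS is censored at last contact, the date of a treatment failure can become evidence of failure-free follow-up. Both effects lower the reported cumulative incidence of failure. The protocol also describes FFS with these three components for the adult randomized trial (1.1.2.1.2) and plans to extrapolate efficacy from that trial (4.1), so readers are likely to set the two side by side.

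**Working it through.** No sample-size or power figure in the plan bears on this point. The check compares the collection window in Protocol Table 8-1 with the FFS horizon.

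**Inputs**
- End of scheduled medication collection: last dose + 30 days, or + 33 with the visit window (Protocol 9.1.5).
- Month length: 30.4375 days (SAP 3.1.1).
- Month 24: Study Day 730 (SAP visit-window table).
- Last-dose days: Day 28 (stop for lack of response), Day 56 (earliest ruxolitinib taper, used as an illustration), Week 24 = Day 168 (planned duration), Week 48 = Day 336 (maximum).

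**Formulas.** Collection ends at last dose + 30 to 33. Uncovered share = 1 − (collection end / 730).

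| Last dose | Collection ends | In months | Uncovered share of 730 days |
|---|---|---|---|
| Day 28 | Day 58–61 | 1.9–2.0 | 92% |
| Day 56 | Day 86–89 | 2.8–2.9 | 88% |
| Day 168 | Day 198–201 | 6.5–6.6 | 72–73% |
| Day 336 | Day 366–369 | 12.0–12.1 | 49–50% |

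**Which FFS time points are exposed**
- 18 months = 18 × 30.4375 = Day 547.9 and 24 months = Day 730.5. Both exceed Day 369, so they lie beyond scheduled collection for every patient treated within the protocol maximum.
- 12 months = Day 365.25. Coverage needs a last dose at about Day 365.25 − 30 = Day 335, so only patients treated to about Week 48 are covered.
- 6 months = Day 182.6. Coverage needs a last dose at about Day 182.6 − 30 = Day 152.6, about Week 22.

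**Size per missed event.** Assume 45 patients in the analysis with full follow-up. One missed failure, in a patient with no other FFS event and no prior cGvHD, lowers cumulative incidence by 1/45 = 2.2 points. The documents give no rate of late new therapy. Purely as an assumed range, 1 to 5 missed patients give 1/45 = 2.2 to 5/45 = 11.1 points.

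**Other endpoints**
- *Day 28 ORR:* stopping treatment before the Day 28 visit is already non-response (SAP 3.5.3).
- *Day 56 durable ORR:* a last dose at Day 28 or later keeps collection open to about Day 58, past Day 56.
- *Duration of response:* censored at the last response assessment (SAP 3.7.1), and Table 8-1 schedules none at Months 12, 18 or 24. With a last dose at Day 168, the last scheduled assessment is also about Day 168, before collection closes at Day 198, so there is no gap. A responder who stopped at Day 56 and kept visits to Week 24 would have a gap of 168 − 89 = 79 to 168 − 86 = 82 days.
- *Relapse and death:* followed to Month 24.

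**The case against.** The strongest reply is that the SAP itself never stops the search. Section 6.4.3 has no end date. Sections 3.4.2.4 and 3.4.2.5 send steroids and CNIs to the concomitant medication page after end of treatment, and 3.4.2.7 provides for flagging therapies that start after the on-treatment period, so later entries are expected. The cut-off rests on one row of Table 8-1, and such rows are not always a hard stop: the adverse event row has the same wording, yet Protocol 8.5.4.8 has second malignancies monitored to 24 months and reported as adverse events.

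Next, Table 3-2 does not name a CRF page for the post-discontinuation row, and its condition (a medication or procedure term is present) would also fit pages that 6.4.3 already searches. Finally, late events may be few. Protocol 1.1.1 places most aGvHD within 100 days of transplant, cGvHD is a competing event, and patients who fail at Day 28 would usually be retreated inside the 30-day window.

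Much of this stands. It rules out saying that failures after safety follow-up are certainly lost, or that a distinct page certainly exists, and it leaves the size open. It does not close the gap. Table 3-2 lists the source apart from the concomitant medication record, 6.4.3 does not name it, and nothing in either document says that aGvHD therapy started during long-term follow-up must be entered where 6.4.3 looks.

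**Conclusion.** The point holds as a gap in the data sources for one FFS component. Followed as written, SAP 6.4.3 can miss new aGvHD therapy started after discontinuation, and the last-contact rule can turn the same date into failure-free time. Any error runs in one direction: it understates the new-therapy part of FFS failure. The 18- and 24-month estimates are exposed for all patients treated within protocol, and the 12-month estimate for all but those treated to about Week 48. The size is unknown; 2.2 points per missed patient assumes 45 patients, full follow-up, and no other FFS event or prior cGvHD.

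A reader might infer three stronger things, none of which the documents support:
- that no later failure is counted; the SAP has no stop date and allows some later medication entries;
- that duration of response has the same long blind period; its censoring rule confines any gap mainly to patients who stop early but keep their visits;
- that the bias can be given as a number of points; that needs a count of late therapies, which neither document supplies.

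FFS is a secondary endpoint in a study without hypothesis tests. Day 28 ORR, Day 56 durable ORR and the relapse and death components are essentially unaffected. The correction is still worth making, because the possible error is one-directional and the remedy is cheap.

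**What to change.** In SAP 6.4.3, add the post-discontinuation aGvHD treatment source of Table 3-2 to the sources for the new-therapy event (mainly for FFS), and state how long it is collected.

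If it is not collected through Month 24, choose one of two courses and say so in SAP 3.7.1 and 3.7.2:
- censor FFS for each patient at the end of therapy collection, noting that this date depends on when ruxolitinib stopped, so the censoring may be informative; or
- report FFS only over the horizon that therapy collection covers.

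The cost is SAP wording and one check of the CRF to confirm where the source sits and until when it is completed. Design and sample size do not change.
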